6.0 Recruitment

The purpose of pre-screening is to identify potentially eligible participants and those who will soon become eligible in order to identify who to approach about the study. Prescreening will consist of (1) reviewing and abstracting clinical rosters and medical records onto a prescreening log to identify and track potentially eligible participants and (2) consulting with clinical providers who can inform on eligibility criteria. The study RA in consultation with the site PI are responsible for reviewing clinical rosters and medical records and consulting with clinical providers on potentially eligible participants.

When feasible, a provider will introduce the study to the caregiver/parent to see if they are interested in learning more using a standardized recruitment script. Because of their volume of patients, it may not be practicable for a provider to always introduce the study. On these occasions, the RA will approach the potential participant after establishing eligibility via records and via consultation with the provider. The RA will approach the caregiver/parent and provide a brief overview of the study using the recruitment script noted above. If the caregiver/parent is interested, the RA will assess eligibility criteria. For those interested and eligible, the RA will proceed with consent.

Some caregiver-infant pairs approached may not be eligible at the time screened, but may become eligible in the future (e.g. infant not yet indicated for cup feeding). We will seek verbal permission to re-approach those interested who are not eligible but maybe come eligible. Those who indicate they are not interested will not be re-approached.

7.0 Consent process

Informed consent is a process that is initiated prior to the individual agreeing to participate in the study and continues throughout study participation. Discussion of risks and possible benefits of study participation will be conducted with the caregiver. A consent form describing the study procedures and risks will be given to the caregiver. The potential risks and benefits and study activities will also be provided to caregivers orally. To ensure privacy for the consent process, we use a nurse manager room to conduct the consent process. Alternatively, we will use a screen to increase privacy on the ward if the room is not available for some reason.

We will obtain consent from the caregiver (typically the mother). Although the mother may not be able to participate in the study, she may be able to consent for the infant and identify a relative caregiver. In cases where the mother is unavailable, we will seek consent from the father of the infant and he will identify a relative caregiver. We will then seek consent for the relative caregiver (an aunt or grandmother). To accommodate this, we would like to revise the consent form to include two statements at the end that the person can tick as noted:

I am the parent of the child.

I am the caregiver of the child.

In cases where the mother (both parent and caregiver) is unavailable, we will use two forms for one infant to show consent of the parent (father) and consent of caregiver (aunt or grandmother).

After reading the consent in English to the potential participant, the person consenting will also explain in Twi if desired. The RAs will be bilingual and able to provide accurate Twi translation. Consent forms will be reviewed with the caregiver/parent orally. The research staff will explain the research study to the caregiver/parent and answer any questions that may arise. The caregiver/parent will sign the informed consent document prior to any study-related assessments or procedures. Caregivers/parents will be given the opportunity to think about it prior to agreeing to participate.

A copy or duplicate of the signed informed consent document will be given to the caregiver/parent for their records. A copy is a photocopy of the original signature consent. A duplicate is a second consent form with all originally signatures. A duplicate will be used when a copier is not readily available. The rights and welfare of the caregiver/parent will be protected by emphasizing to them that the quality of the infant's clinical care will not be adversely affected if they decline to participate in this study. The caregiver/parent may withdraw consent at any time throughout the course of the study.

Informed consent will take place *at least* 24 hours after the birth of the child to allow for birth related care to take place, including the identification of the infant as preterm. The RA will obtain permission from the health care provider to approach the caregiver/parent about the study as part of the screening process. Those participants unable to write their name have the option of providing a fingerprint and having the RA write in their name. Fingerprint consent will be observed by a witness who will also sign the consent form. The consent witness will be an impartial witness and not a family member. We have identified several types of individuals that could serve as impartial consent witnesses for mothers who are not literate. These include the following: (1) hospital administrators, (2) technology support individuals, (3) nurses on other surgical or medical wards (those in the mother-baby unit will not serve as consent witnesses), or (4) records officers.

8.0 Study product(s)

The Nifty Feeding Cup by Laerdal will be the version of the NIFTY cup used for this study. The Nifty Cup manufactured by Laerdal Global Health (see:

<http://www.laerdalglobalhealth.com/doc/2576/Nifty-Feeding-Cup#/Info>) is a reusable product for feeding breast milk to newborns with breastfeeding difficulties (Figure 1). It is a simple to use, easy to clean and culturally appropriate feeding solution which allows the infant to control the pace of feeding. Product specifications are as follow:

- Reusable for use by multiple newborns
- Suitable for reprocessing with the following methods:
 - Steam autoclaving at 136 °C, 10-20 minutes
 - Chemical disinfection with 0.5% chlorine solution, 20 minutes, and rinsed 3 times with clean water afterwards
 - Boiling in water, 10 minutes
- Made with silicone rubber
- Safe for food contact according to *USFDA 21 CFR 177.2600 regulation* Mass: Approx. 23.5 g
- Volume: 5 to 40 ml; the cup has tick marks every 5ml and numerals every 10 ml

- Operating Temperature: -18 °C to +50 °C
- Storage temperature: -40 °C to +60 °C
- Not made with natural rubber latex

For every batch of silicone materials used in the Nifty feeding cup by Laerdal, material samples are sent to an independent test lab for testing to USFDA requirements applicable for food contacting rubber materials, 21 CFR 177.2600.

In all geographies, the Nifty Cup is being commercialized by the manufacturer as a cup for general infant feeding and not a medical device. To implement this decision, Laerdal Global Health:

- o Will only label/promote it for general infant feeding—there will be no references to specific health conditions such as cleft palate or other facial abnormalities
- o Will include “not for medication dispensing” in the use instructions and possibly on the cup itself
- o Will comply with all applicable US and European regulations for food contact materials

The proposed study will be conducted in Ghana, in its entirety. As the USFDA does not have jurisdiction in Ghana, the study is not subject to the USFDA regulations. We are consulting with the Ghana FDA to determine the documentation necessary to conduct this study in Ghana. The Ghana FDA has reviewed this protocol.

The generic cup that will be used in this study is a small medicine cup 30 ml in size (Figure 2). Small medicine cups are manufactured by a variety of manufacturers and are commonly used in health facilities to feed breastmilk to infants who are having breastfeeding difficulties. The cups are generally translucent, calibrated with a variety of measurements including 2.5-30 mL.

Figure 2: Generic medicine cup

9.0 Risks

Potential study risks are minimal. We will not withhold any standard of care procedures. Our study procedures are non-invasive. Infants prescribed cup feeding by the clinical team will still be cup fed, which is the standard of care at KATH. The Nifty Feeding Cup has been evaluated in several infant populations in India and Tanzania and has been shown to be preferred by providers

and caregiver over conventional cups ([name], et al, unpublished data). The Nifty Feeding Cup, with its unique design, minimizes typical problems with cup feeding such as spillage, coughing or aspirating on milk. Because generic cups pose the same risk and the NIFTY™ is specifically designed to reduce these risks, this research involves minimal risk.

Other risks pertain to the caregiver potentially feeling uncomfortable answering questions or being watched while feeding their infant. There is potential for lack of privacy around participation since we will conduct study visits at bedside. There is a risk of loss of confidentiality, though every effort will be made to protect patient identity.

10.0 Mitigation of risks

Caregivers will be provided a standardized set of instructions by the research assistant on how to cup feed prior to beginning to cup to feed their infant. This should minimize adverse effects of cup feeding in general. Caregivers/parents will be told that they are free to refuse to answer any item in any survey and free to decline participating in the study at any time and for any reason including lack of privacy without affecting their clinical care.

We will code all study data for each participant with a unique study identification number (ID). This will minimize use of personal identifiers but maintain the ability to link across sources of data collected from an individual study participant. We will use the Research Electronic Data Capture (REDCap) software to enter and store study data (see Data Capture Methods below). All electronic data will be protected using password-protected computers and will be protected by being stored on a HIPPA compliant server housed within the Institute for Translational Health Sciences (ITHS). Hard copy forms will be maintained in a locked filing cabinet. No individual-level data will be reported on study participants. These procedures will minimize the risk of loss of confidentiality.

11.0 Benefits

Caregiver-infant pairs may benefit by using the Nifty Feeding Cup and by being able to keep the Nifty Feeding Cup after the study for long-term use. Long term use of the Nifty Feeding Cup has the potential to improve health and reduce the risk of death. The additional benefits of this study to science, clinicians, participants, and the public are substantial. This will be the first comprehensive clinical study to examine the Nifty Feeding Cup. There are 9 million infants born with breastfeeding difficulties each year in South India and Africa. Most are preterm and preterm infants often have difficulty breastfeeding and need a supplement feeding tool. If effective, the Nifty Feeding Cup has widespread promise for being established as a standard of care cup for these infants with high impact to the health and survival of millions.

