2.2 Aim and Hypotheses

We aim to compare the Nifty Feeding Cup to a standardized, generic cup in up to 200 caregivers and their preterm infants. We will test the hypotheses that Nifty Feeding Cup feeding compared to generic cup feeding will result in:

Primary:

1. Less spillage.
2. Greater caregiver satisfaction

Secondary:

3. Greater intake of milk (accounting for spillage, exploratory)
4. Shorter feeds (exploratory)
5. Greater caregiver satisfaction 4 weeks post-discharge

Our aim and hypotheses were selected based on the most informative outcomes given the scope of the funding. The above hypotheses are framed in terms of the statistical alternative which is typically more intuitive to non-statisticians.

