3.1 Statistical Analysis

The data analyst will be blinded to the cup assignment. We will use generalized estimating equations for a crossover design to assess intake, spillage, and feeding duration and a sign test to assess the caregiver’s preference. Covariates may include factors such as amount of prior feeding, type of nutrition, number of prior cup feeds with assigned cup, and number of cup feeds between measured feedings. Most covariates typically accounted for (maternal age, other demographics) will not be included because the comparison is the same caregiver/infant pair.

We will conduct exploratory analyses stratifying on age (0-14 days and 15-28 days) and gestational age (<34 weeks and 34-36 weeks) to evaluate potential effect modification by these factors. These are exploratory since this study was not powered to detect effect modification. For each cup separately, we will compare estimates for those assigned the cup first to estimates for those assigned the cup second to evaluate for design effects. If design effects are observed we will analyze our data comparing those first assigned the Nifty cup to those first assigned to the medicine cup, dropping the data from the second cup and removing the cross over design from our study. We will use Stata 13.0 for all statistical analysis. Consistent with our power calculations, a two-sided p-value of 0.05 will be used.

A strength of our statistical approach is that participants with outcome data for at least one feeding assessment are able to be included in our GEE analyses even if other time points are missing. We will evaluate the potential effect of other missing data on our associations using multiple imputation methods.¹²

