5.2.2 Outcomes

Outcomes related to intake, spillage, and duration will be measured at each Feeding Assessment, which will take place at Visit 2 through 5. Caregiver satisfaction will be measured during Feeding Assessment related to the experience of that feed (V2-V5). Caregiver satisfaction will be measured with the In-Hospital Preference Survey (V5) and the Follow-up Survey (V6).

Milk Intake. We will measure amount (in ml) and weight (in grams) of milk in the cup before the feeding. We will measure the amount and weight of milk in the cup after the feeding. If the cup is refilled, we will measure the amount and weight before and after the refill. The amount and weight will be recorded on the Feeding Assessment case report form. We will use a digital scale

to determine all weight measurements. The weight per ml will be estimated based on the baseline measure and used to adjust the gross measure of intake by subtracting out spillage that occurred during the feed. We will calculate intake per feed from these measures less the amount spilled.

Spillage. We will account for spillage of milk by using a baby bib cloth for all feedings. Each caregiver-infant pair will be provided with a bib cloth for each observed feeding. The bib cloth will be weighed before and after each feed and the weights recorded on the Feeding Assessment form. The difference between the pre and post weights will be used as the measure of the amount spilled. A digital scale will be used and milk weight will be in grams. Spillage will be reported as a percent with the amount of milk in grams spilled/mopped up divided by the total amount of milk weighed in grams less the total amount of milk not used.

Caregiver Satisfaction. Our primary measure of caregiver's satisfaction will be the cup she prefers [secondary] and rated satisfaction [primary] which will be recorded in the In-Hospital Preference Survey completed after the caregiver has finished the feeding portion of the study (V5). A secondary measure will be what the caregiver reports uses most of the time measured in the Follow-up Survey 4 weeks post-discharge (V6). We will also measure the caregiver's satisfaction with each cup after each feeding measured in the Feeding Assessment and in the In-Hospital Preference Survey (V2-V5).

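### The protocol writes the participant benefit for the Nifty cup only, has benefits told to caregivers before they rate both cups on a primary subjective outcome, and requires no neutral presentation

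*Combined protocol and SAP*

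**What the plan says.** **What caregivers are told, and when.** Section 7.0 states: "Discussion of risks and possible benefits of study participation will be conducted with the caregiver", and "The potential risks and benefits and study activities will also be provided to caregivers orally". It places this ahead of all data collection: "The caregiver/parent will sign the informed consent document prior to any study-related assessments or procedures". Section 15.2.2 adds that the form is read out because most caregivers will not be literate, so the spoken account carries most of the information.

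**How the benefit is written.** Section 11.0 says pairs may benefit from using and keeping the Nifty cup, and continues: "Long term use of the Nifty Feeding Cup has the potential to improve health and reduce the risk of death". It names no benefit of the generic cup, although Section 18.0 lets caregivers keep both. In arguing that risk is minimal, Section 9.0 says: "The Nifty Feeding Cup, with its unique design, minimizes typical problems with cup feeding such as spillage, coughing or aspirating on milk". It also reports that providers and caregivers preferred the Nifty cup in unpublished work.

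**What is then measured.** Primary hypothesis 2 in Section 2.2 is "Greater caregiver satisfaction". Section 5.2.2 makes its primary measure "rated satisfaction [primary] which will be recorded in the In-Hospital Preference Survey", completed at Visit 5 after both cups have been used, and tags cup preference as secondary. Hypothesis 5, a secondary one, is satisfaction four weeks after discharge.

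**Who is masked.** Section 3.1 says: "The data analyst will be blinded to the cup assignment". No masking of the caregiver or the research assistant is described. The assistant obtains the assignment, hands over each cup and conducts the Visit 5 survey (Sections 5.1.1 to 5.1.5).

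**The concern.** A rating given by an unmasked caregiver is open to expectation, and to courtesy towards the staff who recruited her. A statement before the first feed that one of the two cups may improve health or survival would push ratings towards that cup. The push would have the same direction whichever cup came first, so randomising the order would not balance it.

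The outcomes most exposed are rated satisfaction (primary), stated preference (secondary) and satisfaction at follow-up (secondary). Spillage is weighed and duration is timed, so both are less exposed, though how the caregiver handles each cup could still respond to expectation.

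Section 1.4 describes this as the first comparative study of the cup, and the protocol presents no health or mortality data for it. A one-sided benefit statement therefore has no support within the document, and it could inflate the result of a primary hypothesis.

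**Working it through.** **Step 1: link the sections.**

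- Benefits are told at consent, before any assessment (7.0).
- The only cup-specific participant benefit written down concerns the Nifty cup (11.0).
- The caregiver later rates both cups, unmasked, as a primary outcome (2.2, 5.2.2, 3.1).
- No section requires neutral or balanced wording in the consent discussion, recruitment script or videos.

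**Step 2: does the design remove a suggestion that favours one cup?** Write the expected rating of the generic cup in period j as μ + π_j and of the Nifty cup as μ + π_j + τ + δ. Here τ is the true difference and δ is the shift due to suggestion.

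- *Crossover contrast.* Nifty minus generic is τ + δ + (π_1 − π_2) in one sequence and τ + δ + (π_2 − π_1) in the other. The average is τ + δ, so δ stays.
- *Design-effect check (3.1).* This compares each cup used first with the same cup used second. For the Nifty cup: (μ + π_1 + τ + δ) − (μ + π_2 + τ + δ) = π_1 − π_2. The shift cancels, so the check cannot detect it.
- *First-period fallback (3.1).* (μ + π_1 + τ + δ) − (μ + π_1) = τ + δ, so δ stays.

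**Step 3: illustrative size, preference (secondary outcome).** Section 3.1 specifies a sign test, two-sided at 0.05. Section 2.3 gives 150 pairs, up to 200. Assume that every caregiver states a preference, that there is no true preference, and that suggestion moves the probability of choosing the Nifty cup from 0.50 to p. The exact test rejects when the Nifty count X ~ Binomial(n, p) is ≤62 or ≥88 (n = 150), or ≤85 or ≥115 (n = 200).

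| Assumed split | n = 150 | n = 200 |
|---|---|---|
| 50:50 | 4.1% | 4.0% |
| 52:48 | 6.6% | 7.3% |
| 55:45 | 20.7% | 26.2% |
| 60:40 | 66.3% | 78.7% |

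**Step 4: illustrative size, rated satisfaction (primary outcome).** Section 3.1 names no test for the rating. Section 2.3 says its paired t-test power calculation also covers satisfaction, so that test is used here with the correlations given there (ρ from 0.02 to 0.5). With τ = 0 and δ = b standard deviations of a single rating, the noncentrality is b√n / √(2(1 − ρ)). For b = 0.1 and n = 150 this is 0.1 × 12.25 / 1.40 = 0.87 at ρ = 0.02, and 0.1 × 12.25 / 1 = 1.22 at ρ = 0.5. The critical value is 1.976 on 149 df.

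| Assumed b | ρ = 0.02 | ρ = 0.5 |
|---|---|---|
| 0 | 5.0% | 5.0% |
| 0.05 | 7.2% | 9.3% |
| 0.1 | 14.0% | 22.9% |
| 0.2 | 41.2% | 68.2% |
| 0.3 | 74.1% | 95.5% |

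The documents give no value for p or b. For any fixed shift, more pairs raise the false-positive rate.

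**The case against.** The strongest objection is that the link to the caregiver is unseen. Section 7.0 requires benefits to be discussed, but it does not say that Section 11.0 or Section 9.0 is read out. Section 11.0 also argues the value of the study to science and the public, which reads as text for an ethics board. The consent form and recruitment script are separate attachments that were not available, and they may already be neutral. This stands. A reader might infer that mothers are told the Nifty cup lowers the risk of death, but the documents do not show that. Their absence from the reviewed text is also not a fault in the plan.

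The Section 11.0 sentence is hedged as well: it speaks of long-term use and of potential. Reading it as a claim that the cup does improve health or survival goes beyond the text. Similarly, the Section 9.0 statements support a minimal-risk classification, and nothing says they are passed on to caregivers.

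On size, a 52:48 shift leaves the sign test at 6.6% with 150 pairs, close to nominal, and that test concerns the secondary outcome. This stands too, which is why the range starts at no shift and the rating is shown separately.

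The protocol has some protection: each cup has its own instruction video (5.2.1), the recruitment script is standardised (6.0), and weighed spillage and the cup mostly used at four weeks allow partial corroboration. Standardised wording is not necessarily neutral wording, however, and corroboration from other outcomes does not correct a satisfaction rating.

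**Conclusion.** The concern holds as a gap in the protocol. It requires benefits to be told, writes the participant benefit for one cup, and sets no rule of neutral presentation ahead of an unmasked, caregiver-rated primary outcome. If the benefit wording reaches caregivers, the resulting shift favours the Nifty cup in both sequences and survives the crossover analysis, the design-effect check and the first-period fallback.

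The size is unknown. Under assumed shifts with 150 pairs, the false-positive rate runs from close to nominal (7% at 52:48 for preference; 7% to 9% at 0.05 SD for the rating) to most trials (66% at 60:40; 74% to 95% at 0.3 SD). These figures show sensitivity and do not estimate the bias.

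A reader might infer that any positive satisfaction result would be uninterpretable. The documents do not support that: the wording actually used is not known, and the less exposed outcomes give some corroboration. The change is worth making because it is cheap and because the planned analysis cannot remove the shift once caregivers have been told.

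**What to change.** 1. **Section 11.0:** reword the participant-benefit sentences so that no health or survival advantage of the Nifty cup is offered as a benefit of taking part. The wider rationale for the study can stay if it is clearly separated from benefits to participants.
2. **Section 7.0:** add that the consent discussion, recruitment script and instruction videos describe both cups neutrally. Suggested content: two cups are being compared, it is not known which is better, and the caregiver will keep both.
3. **Section 7.0:** add that the Section 9.0 statements on spillage, coughing, aspiration and earlier preference are not conveyed to caregivers before Visit 5.
4. Check the existing consent form, script and videos against this rule. If they already comply, the protocol text is all that changes.

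Relabelling the cups in the Visit 5 survey by order of use is not recommended: the caregiver has just used both, so it would mask nobody.

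The cost is an IRB amendment, with re-approval of any caregiver-facing text that changes. No visits, staff or participants are added.
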